6.8. Hypotension Management

In the event of recurrent intra-dialytic hypotension or serious hypotension not attributable to acute events (see **Section 3.2.2** for definitions of intra-dialytic hypotension and serious hypotension), study investigators will review the participant's non-study anti-hypertensive medications, dry weight, and volume status. The participant's clinician will be contacted to

consider the following interventions listed in the preferred order of implementation:

- 1) Decrease non-study anti-hypertensive medication(s)
- 2) Increase dry weight if there is no evidence of peripheral or pulmonary edema
- 3) Reduce ultrafiltration rate by increasing dialysis session duration
- 4) Reduce dose of study drug if:
 - a. Peripheral or pulmonary edema is present
AND
 - b. There are no other anti-hypertensive medications prescribed OR other anti-hypertensive medications should not be discontinued (e.g., beta blocker following myocardial infarction)
- 5) Discontinue study medication at the 3rd dose reduction

Treating clinicians will be free to manage hypotension according to standard clinical practices and are not obligated to follow the study guidelines with respect to non-study medication, fluid removal rate, or dry weight. In contrast, dose reduction or discontinuation of study drug will be directly managed by study staff in accordance with the guideline.

6.9. Hyperkalemia Management

[figure not shown]
Serum potassium will be measured at 3-5 days and 2 weeks after study drug initiation or dose increase as well as monthly throughout the duration of treatment. In order to minimize the risks of hyperkalemia, all participants will be provided with standardized, routine printed dietary information about dietary sources of potassium at the Baseline/Randomization visit. Treating clinicians will continue to manage the dialysate potassium concentration according to local standards. A hyperkalemia management guideline will be provided to treating clinicians. Study staff will monitor potassium values and contact treating clinicians in the event of hyperkalemia to review the management guidelines and ensure that hyperkalemia is being actively managed. Treating clinicians will be free to manage hyperkalemia according to local standards. However, study drug dose reductions or discontinuation will be directly managed by study investigators in accordance with the Hyperkalemia Management algorithm (see **Figure 2**).

As shown in **Figure 2**, study drug will be discontinued if serum potassium is ≥ 7.0 mEq/L. Study drug will also be discontinued if a 3rd study drug dose reduction is required. Study drug dose will be reduced if serum potassium is 6.0 – 6.9 mEq/L and either a) remains ≥ 6.5 mEq/L on repeat measurement or b) remains ≥ 6 mEq/L on repeat measurement despite a dialysate potassium bath concentration of ≤ 2.0 mEq/L. Reversible causes of hyperkalemia should be considered and addressed when serum potassium is ≥ 6.0 mEq/L even if there are changes to study drug dosing. Reversible causes of hyperkalemia include vascular access dysfunction, missed dialysis sessions, shortened or technically compromised dialysis sessions, dietary indiscretion and ACEI or ARB use. In general, these reversible causes should be addressed prior to reducing the dialysate potassium concentration. Use of 1.0 mEq/L dialysate potassium is not recommended. However, treating clinicians are not prohibited from using low potassium dialysate solutions in accordance with local practices. Serum potassium will be rechecked within one week when potassium is ≥ 6.0 mEq/L. Results of serum potassium and recommendations for change in dialysis orders will be conveyed to treating clinicians and the dialysis unit nursing staff.

CONFIDENTIAL

Do not disclose or use except as authorized by the Hemodialysis Novel Therapies Consortium.

Figure 2. Management of Hyperkalemia

6.10. Gynecomastia, Gastrointestinal Symptoms or Rash

In the event of persistent gynecomastia/breast tenderness, nausea, vomiting, diarrhea, or anorexia without alternative cause, the dose of study medication may be reduced. Study drug should be discontinued if there is a rash that is not attributable to another cause.

7. Statistical Plan

7.1. Sample Size Determination

Sample size considerations were framed using standard study design parameters to ensure 80% power to detect pre-specified effect sizes utilizing intermediate outcomes. However, for this early phase pilot study, the primary focus is directed at assessing safety and feasibility, with no attempt to create critical test result regions for standard hypothesis testing.

From preliminary studies, we assumed estimated baseline parameters of E' to be 5.8 ± 1.8 cm/s.^{34, 43, 87, 88} Assuming a correlation ≥ 0.2 between pre and post-therapy E' , and a 10% dropout rate of study participants by the end of the study, a sample size of 125 (2:3; 50 patients for the placebo arm and 25 per SPL dose x 3 active treatment arms) will provide 80% power to detect effect size of 0.7SD (1.3 cm/sec) difference in change from baseline to 9 month endpoint in E' , equivalent to a 22% average reduction across the 3 active SPL treatment arms. Short-term studies with SPL in diabetes were consistent with an effect of this magnitude⁵⁴.

For the safety endpoint of hyperkalemia incidence, we assumed a 5% incidence in the placebo arm. With a sample size of 125, derived under the effect size considerations noted previously, this design provides 80% power to detect an average incidence of 22% across the 3 SPL dose arms. Moreover, this same sample size also provides 80% power to detect a small difference of 0.1 mEq/L in time-averaged serum potassium concentration, treated as a continuous variable, between placebo and treatment arms.

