2.1. Primary Objectives

Safety

- To evaluate the safety of chronic spironolactone therapy in individuals with ESRD on HD.
 - Safety events will include the following:
 - Potassium level >6.5 mEq/L
 - Serious hypotension is defined as hypotension requiring hospitalization or treatment in an emergency room and not attributable to overt sepsis, acute myocardial infarction, or other cardiovascular event (e.g. aortic dissection)
 - Serious hyperkalemia defined as hyperkalemia requiring hospitalization, emergency/unscheduled dialysis, or emergency/unscheduled resin therapy
 - The combined incidence of potassium level >6.5 mEq/L or serious hyperkalemia defined as hyperkalemia requiring hospitalization, emergency/unscheduled dialysis, or emergency/unscheduled resin therapy
 - Treatment-emergent events defined as the combined incidence of death, myocardial infarction, stroke, hospitalizations, potassium level >6.5 mEq/L, serious hyperkalemia defined as hyperkalemia requiring hospitalization, emergency/unscheduled dialysis, or emergency/unscheduled resin therapy, and serious hypotension defined as hypotension requiring hospitalization or treatment in an emergency room and not attributable to overt sepsis, acute myocardial infarction, or other cardiovascular event
 - The individual components of the treatment-emergent endpoint
 - Cardiovascular death
 - Hyperkalemia requiring adjustment in dialysate potassium concentration, or discontinuation of study medication
 - Proportion of dialysis sessions utilizing 1 mEq/L potassium dialysis solution bath
 - Within-patient variability in serum potassium concentration
 - Symptomatic inter- or intra-dialytic hypotension

Tolerability

- To evaluate the tolerability of chronic spironolactone therapy in individuals with ESRD treated with hemodialysis
 - Tolerability events will include reduction in dose of study medication during the course of the treatment period or discontinuation of study drug

Efficacy

- To test the hypothesis that chronic blockade of aldosterone with SPL improves diastolic function in individuals with ESRD on HD. The change in E' on TDI echocardiography of the left ventricle from baseline to end of study will be used in the primary endpoint assessment of diastolic function.

Feasibility

- To assess feasibility of conducting a full-scale mortality-powered trial.
 - Feasibility will be assessed based on recruitment rate and dropout rates.

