3.2. Study Endpoints

3.2.1. Primary Endpoints

Safety

The primary safety endpoints are:

- 1) The incidence of serum potassium >6.5 mEq/L
- 2) The incidence of serious hypotension defined as hypotension requiring hospitalization or treatment in an emergency room and not attributable to overt sepsis, acute myocardial infarction, or other cardiovascular event (e.g. aortic dissection).

Tolerability

Tolerability will be assessed on the basis of whether participants can continue the assigned dose throughout the entire treatment period. Any reduction in dose of study medication will be considered a failure of primary tolerability.

Efficacy

The primary efficacy parameters will be measured between baseline and 36 weeks: Change in mitral annular E' velocity will be measured using Tissue Doppler Index (TDI) echocardiography of the left ventricle as a measure of diastolic function and as surrogate measure of left ventricular fibrosis.

E' has been chosen to be the primary echocardiographic endpoint because the intra-observer coefficient of variation is low⁷¹ and multiple studies demonstrate a high correlation with myocardial fibrosis⁷²⁻⁷⁴, a primary biologic endpoint of interest. E', for example, parallels the accumulation of myocardial collagen and fibrosis in the senescence prone mouse⁷⁵, and correlates with endomyocardial fibrosis after human cardiac transplant⁷⁶ as well as the presence of late gadolinium enhancement⁷⁷ – a highly-validated measure of myocardial scar – across multiple disease states. Furthermore, abnormalities in TDI have been strongly linked to mortality in multiple disease states⁷⁸⁻⁸⁰ demonstrating that TDI is a clinically relevant measure. In addition, ESRD-specific studies show that E' is highly correlated with LV mass and other indices of diastolic function, and that changes in E' predict mortality^{34, 81}.

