The primary analysis will examine the intention to treat population. All analyses will be repeated in the as-treated, all-treated and per-protocol populations (see **Section 7.3**). Secondary endpoint analyses will be presented using analogous techniques. $P < 0.05$ will be considered

significant in all analyses.

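### Section 7.1 disclaims critical regions for hypothesis testing, but 7.4.1 calls P < 0.05 significant in all analyses and 2.1 sets a hypothesis to test, with no primary contrast, multiplicity approach or exploratory label

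*Combined protocol and SAP*

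**What the plan says.** Section 7.1 describes the primary focus as safety and feasibility, "with no attempt to create critical test result regions for standard hypothesis testing". The same section chooses the sample size "to ensure 80% power to detect pre-specified effect sizes utilizing intermediate outcomes", without giving an alpha or saying whether tests are one- or two-sided.

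Section 7.4.1 closes with a rule that P < 0.05 counts as "significant in all analyses". Just before that it names the intention-to-treat population as primary and adds: "All analyses will be repeated in the as-treated, all-treated and per-protocol populations".

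Section 2.1 words the primary efficacy objective as a test: "To test the hypothesis that chronic blockade of aldosterone with SPL improves diastolic function".

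Section 3.2.1 lists four quantitative primary endpoints:
- "The incidence of serum potassium >6.5 mEq/L"
- "The incidence of serious hypotension defined as hypotension requiring hospitalization or treatment in an emergency room"
- tolerability, where "Any reduction in dose of study medication will be considered a failure of primary tolerability"
- change in E' from baseline to 36 weeks

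Section 3.1 randomizes 2:1:1:1 to placebo and three doses, and section 7.3 treats the dose-related questions as primary. Neither section 7 nor any other part of the document states a primary contrast, an order of testing, a multiplicity approach, or that P values are exploratory.

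**The concern.** A fixed P < 0.05 rule is a critical region. As written, 7.1 tells the reader that the pilot sets none, and 7.4.1 sets one for every endpoint, primary or secondary. Someone reporting the trial could cite either section.

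Two misreadings are then open. A chance difference on one primary endpoint, or at one dose, could be reported as significant. And a non-significant difference in hyperkalemia or hypotension could be taken as reassurance, although the trial was sized on the three dose arms combined and has much less power for any single dose. The summary at the end of section 1.1 says the results will inform the choice of dose and the design of large trials, so the label would carry weight.

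**Working it through.** **Inputs.** From 7.1: E' SD 1.8 cm/s; pre/post correlation 0.2 (the stated lower bound); dropout 10%; 50 placebo and 25 per dose (75 active); effect 0.7 SD = 0.7 × 1.8 = 1.26 cm/s; hyperkalemia 5% on placebo and 22% on average across active arms. From 7.4.1: threshold 0.05. Assumed, because not stated: two-sided tests.

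**Step 1. The plan's own power figures.**
- SD of change = 1.8 × √(2 × (1 − 0.2)) = 2.277.
- After dropout: 45 placebo, 67.5 active.
- Standard error = 2.277 × √(1/45 + 1/67.5) = 0.438; 1.26 / 0.438 = 2.88.
- Power at two-sided 0.05: 81.3% by noncentral t, 82.0% by normal approximation. This agrees with the stated 80%.
- Hyperkalemia, unpooled z with dropout: 0.17 / √(0.05 × 0.95/45 + 0.22 × 0.78/67.5), which gives 80.9%. Other methods give different values (for example 76.3% by Fisher's exact test without dropout).

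These figures come out only when a 0.05 rejection threshold is supplied. The sizing therefore uses an alpha that 7.1 does not state.

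**Step 2. Chance of at least one false significant primary result, unadjusted two-sided 0.05, endpoints assumed independent.**

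One pooled active-versus-placebo test per endpoint, 1 − 0.95^k:

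| Endpoints k | Chance |
|---|---|
| 2 | 9.8% |
| 3 | 14.3% |
| 4 | 18.5% |

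Three doses (25 each) against one shared placebo arm (50): the three contrasts are correlated, so the rate per endpoint was simulated with 2 million normal draws and is 13.5%. Over k endpoints, 1 − (1 − 0.1346)^k:

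| Endpoints k | Chance |
|---|---|
| 3 | 35% |
| 4 | 44% |

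**Step 3. What pulls these down.** Under 6.8 and 6.9, hypotension and hyperkalemia can lead to dose reductions, and any dose reduction is a tolerability failure. Three of the four endpoints are thus linked. Two are binary and may be sparse: with Fisher's exact test, 50 versus 25 and a true rate of 5% in both arms, the actual type I error is about 2%. Section 7.4.1 names logistic or Poisson regression for the primary safety endpoints, so this only illustrates that the nominal 5% per test may not apply.

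**Step 4. What a non-significant result at one dose would mean.** With 25 versus 50 and the plan's 22% versus 5%, power before dropout is about 54% by Fisher's exact test and 49% by unpooled z. For E' at 1.26 cm/s with dropout (22.5 versus 45), it is about 56% by noncentral t. A true difference of the planned size at one dose would be missed a little under half the time, or about half by unpooled z.

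**The case against.** The strongest defence is that 7.1 concerns sizing and sets no trial-level decision rule, while P < 0.05 is an ordinary reporting convention. The document speaks throughout of pilot data and pilot estimates, makes no confirmatory claim, and says in 7.4 that methods may be revised. Early-phase pilots commonly leave P values unadjusted.

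Part of this stands. Lack of multiplicity control is not in itself a fault here, and 7.1 does not expressly forbid calling a result significant. But the pilot language is never attached to the P values, and a general reservation that methods may change does not say which section governs.

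A reader might also infer larger figures than the plan supports:
- **Twelve independent tests.** Four endpoints by three doses would give 1 − 0.95^12 = 46%. The plan specifies no pairwise dose tests: 7.4.1 refers only to a treatment factor, and 7.1 powers the average of the active arms. The dose contrasts share a placebo arm, so they are not independent in any case.
- **Four populations as a further multiplier.** Sections 7.3 and 7.4.1 make intention-to-treat primary. The others are secondary and overlap heavily with it.
- **Tolerability as a certain fourth test.** Section 7.4 assigns it no test, hence *up to* four endpoints.
- **A plan to treat non-significance as safety.** No section proposes this. The risk lies in how an unqualified rule would be read.

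**Conclusion.** The concern holds as an unresolved conflict between 7.1 on one side and 7.4.1 and 2.1 on the other, made worse by the missing primary contrast. Under independent endpoints and two-sided 0.05, the chance of at least one false significant primary result is about 19% with a pooled contrast on four endpoints and up to about 44% with three dose contrasts on each. Both are upper-end illustrations: linked endpoints, sparse events and a count of three tested endpoints all reduce them. The plan does not say which contrast applies, so no single figure can be assigned. The effect is on how results are interpreted and reported, not on conduct of the trial.

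**What to change.** 1. In 7.4.1, replace the blanket P < 0.05 rule with effect estimates and 95% confidence intervals. State that any P values are nominal and unadjusted and that no confirmatory claim will be made.
2. Add that a non-significant difference in a safety endpoint is not evidence of safety.
3. Reword the efficacy objective in 2.1 as estimation of the effect on E', in line with 7.1.
4. In 7.1, state the alpha and sidedness behind the 80% power figures, as sizing assumptions only.

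This follows the position the plan already takes in 7.1 and needs wording changes only; sample size, data collection and visits are untouched. The price is that the report cannot label results significant.

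If the sponsor prefers formal testing, the consistent alternative is to withdraw the 7.1 disclaimer and state alpha, sidedness, the primary contrast and a multiplicity approach. That costs power: with Bonferroni over four endpoints (0.05 / 4 = 0.0125 each), the pooled E' test falls from 82% to about 65% by normal approximation.

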7.2. Randomization and Stratification

To ensure balance in treatment assignments within potential confounders, a stratified randomization procedure, blocking on four (4) strata formed by the 2×2 cross-classification of 1) dialysis vintage (≥ 1 vs. < 1 year on dialysis) by 2) ACEI or ARB use (yes, no), within Clinical Centers will be implemented within a web-based randomization module deployed centrally within the DCC. Within each of these strata, participants will be randomly allocated to the placebo and the three SPL dose arms with the ratio of 2:1:1:1.

The treatment assignment code, corresponding to each treatment identifier number, will be known only to the person serving as the DCC Quality Assurance Director and the IDS, until the completion of treatment and data collection on all participants. At the end of a patient's study phase, the participants and the treating physicians will be asked to guess their treatment groups, and provide the basis for their judgments for analysis later, to determine whether the blinding has been broken. However, except in the case of emergency unmasking, the treatment codes will not be identified until the DSMB has approved unblinding in preparation for the public dissemination of results.

7.3. Intent-to-treat Analysis and Missing Data

An intent-to-treat analysis, in which all available data on all randomized participants are included, will be used for the primary comparison of treatments. All attempts will be made to keep missing data to a minimum, and participants who withdraw from treatment will be encouraged to continue on study in order to provide complete follow-up information. Thus, irrespective of withdrawal from treatment, all participants should continue to be followed with all scheduled outcome evaluations until the end of the study. However, it is expected that up to 10% of the randomized participants may withdraw prior to the final assessment of response at 36 weeks. These participants will be included in the denominator for evaluation of the response rates defined for the primary endpoint.

The characteristics at the time of randomization for those participants without complete follow-up will be examined; however, there will be limited statistical power to detect any but major differences between these participants and those with complete follow-up. In addition, in order to assess the potential biases introduced by differential withdrawal among treatment arms, a comparison of withdrawal rates and/or time to withdrawal will be included as an ancillary analysis to the primary endpoint comparison.

Secondary analyses will examine the all-treated, as-treated, and per-protocol populations as defined below:

- All-randomized population/intention-to-treat (ITT): Any participant randomized into the study, regardless of whether they received study drug.
- As-treated population: Any participant randomized into the study regardless of whether they received study drug. As-treated participants will be analyzed according to the dose of study drug actually received.
- All-treated population: Any participant randomized into the study that received at least one dose of study drug.
- Per-protocol population: Any participant who was appropriately randomized, and received the protocol-dictated study drug exposure ($\geq 75\%$ of prescribed doses) and endpoint assessments through 36 ± 2 weeks.

Because dose-related efficacy and safety are primary questions of interest in this study, the ITT analysis will be supplemented with an analysis of the as-treated population. Although ITT approaches provide the least-biased analysis of treatment efficacy and safety, as-treated analyses provide important complementary information on biological effectiveness of therapy (e.g. theoretical efficacy if drug were tolerated by all participants) and on the effects of actual doses used that is not captured by ITT analyses in which the unit of analysis is a randomized therapy that may not have been used by individual participants⁸⁹. For this reason, as-treated approaches provide important complementary information to ITT analyses and are typically mandated as an important secondary analyses of clinical trials by the FDA⁸⁹. Given a treatment protocol that allows for dose reduction of study medications, the as-treated analysis will provide critical information in this trial for assessing dose-related efficacy and the incidence of adverse events such as hyperkalemia. As-treated analyses will assign treatment dose according to the dose used at the time of an adverse event (safety analyses) or according to the mean dose received during the trial (efficacy analysis).

In general, missing data will not be imputed. Every effort will be made to use statistical methods that are robust to missingness, and the number of participants included with each analysis will be given with the results.

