3.1. General Design

This is a randomized, placebo-controlled 4-arm trial that will compare placebo with 3 doses of SPL. Participants will be randomized in a 2:1:1:1 fashion to placebo or SPL, with equal proportions randomized to each of 3 SPL doses: 12.5, 25 or 50 mg once daily. As shown in **Figure 1**, the study will be conducted in 2 phases – a dose escalation phase and a treatment phase.

All participants randomized to SPL will initiate treatment at 12.5 mg daily. Participants will be evaluated weekly for tolerability, hypotension and hyperkalemia. At 2 weeks, if the initial dose has been tolerated, participants randomized to the 25 or 50 mg SPL arm will increase the dose to 25 mg for 2 weeks with weekly evaluation for tolerability, hypotension and hyperkalemia. Participants randomized to 12.5 mg SPL or placebo arm will continue on the same dose with weekly evaluation for tolerability, hypotension and hyperkalemia.

[figure not shown]
At 4 weeks, participants randomized to the 50 mg SPL arm will increase the dose to 50 mg if the 25 mg dose was tolerated with weekly evaluations for tolerability, hypotension and hyperkalemia.

until 6 weeks. Participants randomized to 12.5 mg, 25 mg, or placebo will continue on the same dose with weekly evaluation for tolerability, hypotension and hyperkalemia until 6 weeks.

In order to maintain the blind, during the dose escalation phase all study participants, regardless of randomized assignment, will receive new study drug kits every 2 weeks and will be evaluated weekly.

At the end of the dose escalation phase, participants will continue treatment based on the randomized dose assignment for an additional 30 weeks (treatment phase) such that the total duration of study medication is 36 weeks. As described in **Sections 6.8 and 6.9**, the dose of SPL or placebo will be decreased during the dose-escalation and follow-up phases for hypotension, hyperkalemia or other dose limiting side-effects.

Figure 1. Study Design

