5.2. Treatment Regimen

As depicted in **Figure 1**, 125 participants will be randomized in a 2:1:1:1 fashion to either placebo or SPL (12.5, 25, or 50 mg), with an equal proportion in each SPL group. SPL will be matched with placebo and administered orally, once daily, post-dialysis. Participants will be instructed that, on days of dialysis treatment, the dose should be taken after the dialysis session. All patients will be started on SPL 12.5 mg once daily or matched placebo. Potassium levels will be checked 3-5 days and 2 weeks after initiation of study drug. Dialysis run-sheets will be evaluated weekly for the occurrence of adverse events such as hypotension and gastrointestinal symptoms. Adjustment to dosage of concomitant medications, the dialysis prescription, or study drug for hypotension or hyperkalemia will be made as described in **Section 6.8 and Section 6.9**.

At 2 weeks, in the absence of dose-limiting hyperkalemia or hypotension, subjects randomized to the 25 or 50 mg SPL arm will increase the dose to 25 mg and those randomized to 12.5 mg will continue that dose. At 4 weeks, in the absence of dose-limiting hyperkalemia or hypotension, participants randomized to 50 mg SPL will increase the dose to 50 mg SPL, and participants randomized to 12.5 mg or 25 mg will continue the same dose.

In order to maintain the blind, all study participants, regardless of randomized assignment, will receive a new study drug supply every 2 weeks during the dose escalation phase. For all participants, serum potassium levels will be checked at 3-5 days and at 2 weeks after the new study drug supply is dispensed, and weekly evaluations will be performed for tolerability, hypotension and hyperkalemia.

At the end of the dose escalation phase, participants will continue treatment based on the

randomized dose assignment for an additional 30 weeks (treatment phase) such that the total duration of study medication is 36 weeks. As described in **Sections 6.8 and 6.9**, the dose of SPL or placebo will be decreased or discontinued during the dose-escalation and treatment phases for hypotension, hyperkalemia or other dose limiting side-effects.

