7.4.1. Descriptive Analyses and Primary Efficacy and Safety Analyses

Standard descriptive statistics will be used to summarize baseline characteristics and study outcome measures at each follow-up visit, both overall, and within each treatment group.

Examination of baseline characteristics will include estimates of the distribution of age, race, and other demographic characteristics, lab measures and study center. Summary statistics such as means, medians, and ranges will be produced for all measured variables.

Frequencies will be computed for all categorical and ordinal variables. Graphical methods including stem-and-leaf diagrams and boxplots will be used to examine distributions, identify potential influential points, and guide in the choice of transformations, if warranted. The balance of baseline measures across the three treatment groups will be compared using appropriate k-sample tests, including Kruskal-Wallis tests and Fisher's exact tests.

Analysis of Primary Efficacy and Safety Outcomes Mean (\pm standard deviation) or median (interquartile values) of baseline and end of study measurement in the primary endpoint E' will be presented. Change in E' velocity at 36 weeks will be assessed and reported quantitatively, and descriptive statistics for absolute and % change will be provided. Mixed effects linear regression models with baseline covariate adjustments will be used for assessment of treatment effects. Model assumptions regarding homoscedasticity and normality will be examined using standard techniques.

For the primary safety endpoint, tables with percent incidence and incidence rate (for events that can occur more than once during follow-up) will be prepared. Differences in incidence and incidence-rate will be assessed using logistic regression or Poisson regression with factors for assigned treatment and the stratification variable. In particular, for safety endpoints, we will investigate the potential change in potassium level in placebo and treatment groups with monthly measure of potassium. Mixed effects linear regression models will be used to assess the direction and time averaged magnitude of change in potassium, with and without controlling for baseline covariates. The proportion of serious hyperkalemia in treatment and placebo groups will be compared with Chi-square test or Fisher's exact test.

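### As-treated efficacy by mean dose received does not estimate efficacy had everyone tolerated the drug, and it can create or hide a dose trend; the primary ITT result is unaffected

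*Combined protocol and SAP*

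**What the plan says.** Section 7.3 makes ITT primary and supplements it with an as-treated analysis, which it says informs "theoretical efficacy if drug were tolerated by all participants". It adds that "the as-treated analysis will provide critical information in this trial for assessing dose-related efficacy". The same section ranks the methods: "Although ITT approaches provide the least-biased analysis of treatment efficacy and safety". In the as-treated efficacy analysis, participants are classified "according to the mean dose received during the trial (efficacy analysis"). Mean dose is not defined further, for example for days off drug or missed capsules.

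Dose can change after randomization. Section 5.2 says that it "will be decreased or discontinued during the dose-escalation and treatment phases for hypotension, hyperkalemia or other dose limiting side-effects", and section 3.1 says much the same. Section 5.4 lets the investigator withhold escalation and keeps anyone not at the final dose by Week 12 at the current dose. Sections 6.8 to 6.10 give the reduction and stopping rules; for example, "study drug will be discontinued if serum potassium is ≥ 7.0 mEq/L".

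For the efficacy model, section 7.4.1 states: "Mixed effects linear regression models with baseline covariate adjustments will be used for assessment of treatment effects". It also repeats all analyses in the as-treated population and counts P<0.05 as significant throughout. Section 7 gives no method for post-randomization confounding of dose.

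**The concern.** Efficacy had everyone tolerated the drug is a causal contrast between doses in one population. Mean dose received does not provide it. Within an arm, a participant with a low mean dose is one whose clinical course led to a reduction, a stop or a missed escalation. If that course shares causes with E' change, a slope on mean dose mixes drug effect with prognosis.

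The down-titration table in section 5.4 makes this asymmetric. A placebo participant who is reduced stays at 0 mg, while a spironolactone participant moves toward 0. If those who are reduced also have worse E' change, they collect at the low end and higher dose looks better with no drug effect. If they have better E' change, a real dose effect can be hidden.

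Dose choice is at stake. Section 1.1 says the trial will supply data for choosing an optimal dose and designing larger trials, and section 7.3 counts dose-related efficacy among the primary questions.

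**Working it through.** **Inputs from section 7.1.** E' SD 1.8 cm/s, pre/post correlation 0.2, 10% dropout, 50 placebo and 25 in each of three active arms, effect 0.7 SD (printed as 1.3 cm/s), hyperkalemia 5% on placebo and 22% on spironolactone. The plan does not state sidedness; two-sided 0.05 is used here.

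**Plan's own figure.** SD of change = 1.8 × √(2 × (1 − 0.2)) = 2.28 cm/s. Effect = 0.7 × 1.8 = 1.26 cm/s. With 45 versus 67 completers a two-sample t test has 81.2% power. The required number is 110 / 0.9 = 122.2, so 123 against the planned 125. The stated 80% is reproduced.

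**How mean dose moves over 36 weeks** (escalation at weeks 2 and 4):
- 50 mg arm, completes: (2 × 12.5 + 2 × 25 + 32 × 50) / 36 = 46.5 mg.
- 50 mg arm, cut to 25 mg at week 6: (25 + 50 + 2 × 50 + 30 × 25) / 36 = 25.7 mg.
- 25 mg arm, completes: (2 × 12.5 + 34 × 25) / 36 = 24.3 mg.
- 50 mg arm, stopped at week 6: (25 + 50 + 100) / 36 = 4.9 mg.

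Assigned arm sets most of the spread, but a reduced 50 mg participant lands beside a 25 mg completer, and one who stops early lands near placebo.

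**Simulations with no drug effect.** A latent frailty drives both the liability to a dose cut and E' change. A linear slope on mean dose is tested at 0.05. The cut rates and correlations are assumptions.

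*First set:* 3,000 trials per setting, 45/22/22/22 completers, liability correlated 0.71 with frailty, reduction by one or two levels.

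| Reduced in 12.5/25/50 mg arms | Frailty correlation with E' change | False slope, cm/s per 50 mg | Type I error |
|---|---|---|---|
| 5/10/15% | 0.1-0.3 | 0.04-0.13 | 5.1-5.2% |
| 10/15/25% | 0.1-0.3 | 0.08-0.20 | 5.2-6.1% |
| 15/25/40% | 0.3-0.5 | 0.24-0.40 | 7-10% |
| 25/40/60% | 0.3-0.5 | 0.31-0.55 | 7-11% |

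A further run over correlations 0.1-0.5 gave slopes of 0.05 to 0.64 and error of about 4-13%.

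*Second set:* 20,000 trials per cell, 45/22/23/22 analysed, 5% cut on placebo, one common rate in the active arms. Type I error by correlation between cut liability and E' change:

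| Correlation | 22%, one step down | 22%, stopped | 40%, one step down | 40%, stopped |
|---|---|---|---|---|
| 0 | 5.0% | 5.0% | 5.1% | 5.0% |
| −0.15 | 5.3% | 6.0% | 5.6% | 6.8% |
| −0.35 | 6.8% | 10.6% | 8.5% | 16.5% |
| −0.63 | 10.5% | 24.4% | 16.7% | 44.7% |

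The two scales differ: in the first set, a frailty correlation of 0.3-0.5 implies a liability correlation of 0.71 × 0.3 = 0.21 to 0.71 × 0.5 = 0.36 in size. The −0.63 row is therefore a strong assumption.

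**Comparison with the design effect.** The 1.3 cm/s is an average over the three active arms, whose mean assigned dose is (12.5 + 25 + 50) / 3 = 29.2 mg. A slope per 50 mg must be put on that scale:
- 0.24 × 29.2 / 50 = 0.14 cm/s, and 0.14 / 1.3 = 11%.
- 0.55 × 29.2 / 50 = 0.32 cm/s, and 0.32 / 1.3 = 25%.

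**Analyses that keep randomization, same null.** In the second set, the ITT trend on assigned dose rejects in 4.7-5.2% of trials, and mean dose instrumented by assigned dose rejects in 4.8-5.0% (run with cuts as outright stops), with slope −0.03 to 0.00 per 50 mg. In the first setup, two-stage least squares has bias near 0, error of about 5% and a standard error about 3-12% larger than the mean-dose regression.

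**The case against.** The plan already holds the main safeguard. ITT is primary, the sentence at issue calls it least biased, and the as-treated analysis is secondary. The randomized four-arm comparison is available for dose choice. A reader might infer that the primary efficacy result is compromised; the documents do not support that.

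A reader might also infer that adverse events set mean dose. They modify it; assigned arm drives most of it.

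The inflation may be negligible. The documents give no reduction rates. Where Table 1 in section 1.3 reports hyperkalemia incidence, it is 0-14%. Under section 6.9 a potassium of 6.0-6.9 mEq/L leads to reduction only if it persists on repeat under stated conditions, and section 6.8 lists study-drug reduction fourth. Some causes of hyperkalemia named there, such as missed sessions, access problems and diet, need not reflect cardiac frailty. All this stands, and the low end of the range is about 5%.

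The simulations use a linear slope without baseline adjustment, whereas section 7.3 fixes no functional form and section 7.4.1 adjusts for baseline covariates. Covariates that predict intolerance would remove part of the bias, but they cannot be relied on to capture what happens after randomization.

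Finally, it is tempting to replace the as-treated analysis with two-stage least squares. That estimate largely rescales the ITT contrast and assumes one linear slope, which is awkward in a trial meant to inform dose choice. It belongs beside the other analyses, not in their place.

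None of this rescues the stated interpretation, which fails whatever the size of the bias.

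**Conclusion.** The point holds as a fault of interpretation and labelling in a secondary analysis. A regression on mean dose received, adjusted for baseline covariates only, compares participants who tolerated more drug with those who tolerated less.

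With no drug effect, type I error runs from about 5% to about 10-13%, the upper end needing 40-60% reduced in the 50 mg arm and a frailty correlation of 0.5. It is higher if drug is often stopped outright: 24.4% at a 22% stopping rate under the strongest link tried. These figures depend on assumed rates and correlations.

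Dividing the per-50-mg slopes directly by 1.3 cm/s would suggest 18-42% of the design effect. That mixes scales; 11-25% is the like-for-like figure. Nor does the bias always favour the drug, since the opposite link between intolerance and E' change would mask a real trend.

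**What to change.** In section 7.3:
- Delete the phrase about efficacy if all participants tolerated the drug.
- Keep the mean-dose efficacy analysis, labelled non-randomized and exploratory and not a basis for dose choice. Define mean dose, including days off drug and missed capsules.
- State that dose-response conclusions for E' rest on randomized arm.
- Add two-stage least squares of E' change on mean dose received, with randomized arm as instrument, adjusted for baseline E' and the stratification factors.

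The cost is about one paragraph and a standard procedure. No new data are needed, because sections 4.4.2 and 6.6.1 keep participants who stop drug in follow-up through Week 36, and section 7.4 allows methods to be revised. The downsides to state are a standard error about 3-12% larger, the assumption that arm acts on E' only through mean dose, and a linear dose effect.
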